5.3 INVESTIGATORS RESPONSABILITIES

In collaboration and according to the Standard Operating Procedure (SOP) of the sponsor, a detailed list of delegation of responsibilities has been established. It is held by the sponsor, who is finally responsible for the correct performance of delegated responsibilities by the respective persons or institutions. A copy of this list will be delivered to the participating institutions.

The investigator of each institution undertakes to conduct the study according to the protocol which was approved by the ethics (CCP) and health authorities (ANSM). The

investigator must not make any changes to the protocol without the permission of the sponsor and without the CCP has given a favorable opinion on the proposed amendments.

It is the responsibility of the investigator responsible for the study in the participating centre:

- To provide his curriculum vitae as well as co-investigators
- To identify team members, who will participate in the study and define their responsibilities
- To start recruiting patients after authorization of the sponsor
- To try to include the required number of patients within the period of recruitment

It is the responsibility of each investigator:

- To obtain the informed consent dated and signed personally by the patient before any selection process specific to the study
- To fill in an electronic case report form (e-CRF) for each patient included in the study and allow direct access to source documents to validate e-CRF data . To correct, sign and date the correction(s) of the e-CRF for each patient enrolled
- To notify the sponsor of any SAE(s) within the time required
- To accept regular monitoring visits and possibly those of auditors mandated by the sponsor or inspectors from authorities

All documentation on the study (protocol, consents, notebooks observation, file investigator, etc.) and original documents (laboratory results, x-rays, minutes of consultations, review reports...) must be kept in a safe place and considered confidential material.

The Investigator will maintain the confidentiality of the identity of subjects enrolled in the study and the information contained in the study records.

5.4 SPONSOR RESPONSABILITIES

It is the responsibility of the sponsor to:

- Subscribe insurance to cover its liability for the harmful consequences of research
- Provide the investigators with all information necessary to conduct the research
- Apply for authorization from a relevant CPP
- Apply for authorization from ANSM
- Inform the Directors and Pharmacists of health facilities
- Inform ANSM of any serious incidents that may be due to research

5.5 BIOCOLLECTIONS

Biological samples collected for the immunological assessment will be stored in a biocollection. The patient informed consent will be collected and the samples will be stored in one of the biocollections of Assistance Publique-Hôpitaux de Paris: the Hematology biobank approved by INCa and located at the Saint-Antoine Hospital (Declaration N ° DC-2009-963 and authorization N ° AC-2013-1992).

The Sponsor shall finance the study and endorses a policy of insurance covering the financial consequences of its civil liability in accordance with regulations in order to guarantee against possible damage resulting from the research.

Non-compliance with the Research Legal Conditions is a cause for guarantee exclusion.

5.6 ARCHIVING

The data archiving will be under the responsibility of the investigator and, as required by law.

Data will be kept for a minimum of 15 years after the end of the study.

7. INTRODUCTION

Chronic Graft-versus-Host Disease (GvHD) is one of the most common and clinically significant complication affecting long-term survivors of allogeneic stem cell transplantation (allo-SCT). Chronic GvHD (cGvHD) is the cause of death in up to one third of all long-term survivors after transplantation for leukemia and is consistently associated with decreased quality of life, impaired functional status, ongoing need for immunosuppressive medications and infectious complications. Standard first line systemic treatment for cGvHD is orally administered corticosteroids (prednisolone 1 mg/Kg/d) and cyclosporine, with a median duration reported between 18 and 23 months. Therapy with corticosteroids is often unrewarding and the toxicities from prolonged corticosteroid administration are great. Chronic GvHD emerges from alloreactive processes between donor-derived immune cells and host cell populations. While its pathophysiology is still poorly understood, data in humans support a role of both T and B cells in a highly complex network. How these T- and B-cell networks interact has not been resolved.

Arsenic derivatives have been identified as compounds with therapeutic potential for over 2000 years in Greek and Chinese medicine. The combination of ATO and oral all-trans retinoic acid tretinoin [ATRA] currently constitutes the standard of care for most patients with newly diagnosed and/or relapsed acute promyelocytic leukemia (APL). The use of ATO has also been explored in many other hematologic malignancies and in solid tumors. Its role has also been explored in murine models of autoimmune and autoinflammatory diseases. Chronic GvHD presents clinical features that mimic autoimmune diseases such as systemic sclerosis, lupus erythematosus or Sjögren syndrome, and autoimmune-like manifestations are a defining characteristic of cGvHD. In a murine model of chronic GvHD, ATO effect was mediated through the depletion of glutathione and the overproduction of H2O2 that killed activated CD4+ T cells, in particular Th17 cells, and PDC, two key cells in chronic GvHD pathophysiology initiation. Furthermore, autoantibody production was also inhibited by ATO in this model, suggesting that ATO also triggers B cells death in a phenomenon which cooperates for controlling chronic GvHD.

This leads to the hypothesis that ATO delivered during the course of the disease or even early at diagnosis of chronic GvHD- and possibly in prevention of cGvHD before its detection- will be an effective treatment. To test this hypothesis, we proposed this study of ATO in combination with corticosteroids as first line therapy for newly diagnosed chronic GvHD after allo-SCT. We hypothesized that the addition of ATO to prednisone for the initial treatment of chronic GvHD will increase the overall response rate and enable a more rapid and effective corticosteroids taper. We authorized the use of cyclosporine A, as a somewhat widely adopted measure, due to its use for its supposed possible beneficial action on acute GvHD in the early weeks after allografting and sometimes continuously maintained in spite of recognized inefficacy to influence the course of the autoimmune processes going on under the designation of cGvHD.

8. STUDY OBJECTIVES AND ENDPOINTS

8.1 OBJECTIVES

8.1.1 Primary objective

The primary objective is to improve the response rate (complete and partial remission) at 6 months after diagnosis of chronic GvHD and treatment with arsenic trioxide (ATO) in combination with prednisone with or without Ciclosporin as first line treatment.

The aim of this study is to assess whether ATO allows improving response rate at 6 months after the diagnosis of chronic GVHD from 60% (historical rate) to 85%.

8.1.2 Secondary objectives

The secondary objectives are:

- To evaluate failure-free survival (FFS), defined as death, recurrent or progressive malignancy, or initiation of a new systemic treatment for chronic GvHD
- To decrease non-relapse mortality (NRM) of infectious and non-infectious origin
- To improve overall survival (OS) and progression-free survival (PFS)
- To spare patients from long-term use of corticosteroids (and their long-term side effects)
- To improve quality of life self-reported by patient using the Lee Symptom Scale (LSS) and Functional Assessment of Chronic Illness Therapy with Bone Marrow Transplantation subscale (FACT-BMT)
- To evaluate tolerability and safety of ATO in combination with prednisone, with or without Ciclosporin, in patients with chronic GvHD after allo-SCT.

8.2 ENDPOINTS

8.2.1 Primary endpoint

The primary endpoint is the evaluation of response rate (CR and PR) at 6 months after the first ATO infusion, with no secondary systemic therapy at any time before M6.

NIH grade of chronic GVHD will be used for the exact definition of this endpoint.

- Complete remission (CR) is defined as complete disappearance of any sign of chronic GvHD
- Partial remission (PR) is defined as improvement of 1 or more point on a 4 to 7-points scale or an improvement of 2 or more points on a 10 to 12-points scale in at least 1 organ or site without progression in any other organ or site.
- More details for response determination are given in the following table:

Organ	Complete Response	Partial Response	Progression
Skin	NIH Skin Score 0 after previous involvement	Decrease in NIH Skin Score by 1 or more points	Increase in NIH Skin Score by 1 or more points, except 0 to 1
Eyes	NIH Eye Score 0 after previous involvement	Decrease in NIH Eye Score by 1 or more points	Increase in NIH Eye Score by 1 or more points, except 0 to 1
Mouth	NIH Modified OMRS 0 after previous involvement	Decrease in NIH Modified OMRS of 2 or more points	Increase in NIH Modified OMRS of 2 or more points
Esophagus	NIH Esophagus Score 0 after previous involvement	Decrease in NIH Esophagus Score by 1 or more points	Increase in NIH Esophagus Score by 1 or more points, except 0 to 1
Upper GI	NIH Upper GI Score 0 after previous involvement	Decrease in NIH Upper GI Score by 1 or more points	Increase in NIH Upper GI Score by 1 or more points, except 0 to 1
Lower GI	NIH Lower GI Score 0 after previous involvement	Decrease in NIH Lower GI Score by 1 or more points	Increase in NIH Lower GI Score by 1 or more points, except from 0 to 1
Liver	Normal ALT, alkaline phosphatase, and Total bilirubin after previous elevation of 1 or more	Decrease by 50%	Increase by 2 × ULN
Lungs	- Normal %FEV1 after previous involvement - If PFTs not available, NIH Lung Symptom Score 0 after previous involvement	- Increase by 10% predicted absolute value of %FEV1 - If PFTs not available, decrease in NIH Lung Symptom Score by 1 or more points	- Decrease by 10% predicted absolute value of %FEV1 - If PFTs not available, increase in NIH Lung Symptom Score by 1 or more points, except 0 to 1
Joint and fascia	Both NIH Joint and Fascia Score 0 and P-ROM score 25 after previous involvement by at least 1 measure	Decrease in NIH Joint and Fascia Score by 1 or more points or increase in P-ROM score by 1 point for any site	Increase in NIH Joint and Fascia Score by 1 or more points or decrease in P-ROM score by 1 point for any site
Global	Clinician overall severity score 0	Clinician overall severity score decreases by 2 or more points on a 0-10 scale	Clinician overall severity score increases by 2 or more points on a 0-10 scale

ULN indicates upper limit of normal.

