Lungs (Liters and % predicted) 
 
• Bronchiolitis Obliterans
 
	FEV1	FVC	Single Breath DLCO (adjusted for hemoglobin)	TLC	RV	
Liver Values	Total serum bilirubin mg/dL	ULN mg/dL	ALT U/L	ULN U/L	Alkaline Phosphatase U/L	ULN U/L
Baseline Values	Total Distance Walked in 2 or 6 Mins:   2 min  6 min	Karnofsky or Lansky	Platelet Count K/uL	Total WBC K/uL	Eosinophils %	
	 Abnormality present but explained entirely by non-GvHD documented cause (specify site/alternate cause): _____  Abnormality present but explained entirely by non-GvHD documented cause (specify site/alternate cause): _____  Abnormality present but explained entirely by non-GvHD documented cause (specify site/alternate cause): _____					

[figure not shown]

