11.4.2 Secondary Endpoint analyses

11.4.2.1 Response by organ

The proportion of response at 6 months (Complete, partial or progressive) will be estimated and presented for each organ. No response is evaluated for an organ when no abnormalities is present at V1, except progressive disease.

Derivation

Derived variables	Definition
Complete response for each organ	Cf Appendix 1 “Evaluation de la réponse – 19OCT2020”
Partial response for each organ	
Progressive disease	
Organ not involved at any moment	

The following table will be presented:

Organ	Response at M6	FAS Population (N = XX)
Organ 1	Complete response	n/N (XX.X%)
	Partial response	n/N (XX.X%)
	Progressive disease	n/N (XX.X%)
	Organ not involved at any moment	n/N (XX.X%)

This table will be completed for skin, mouth, lung, eyes, gastro-intestinal, liver and joint & fascia.

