17. APPENDICES

17.1 RESPONSE CALCULATION ALGORITHM

Etude GMED_16_001 : Evaluation des réponses complètes et partielles – 19/10/2020

Les réponses sont définies comme (règles de calcul basées sur le protocole et l'article Lee et al)

- Complete response at a visit: Lorsque tous les scores de « cGVHD activity assessment form A » des organes suivants sont à 0 ou que la variable "abnormalities present but explained entirely by non-GVHD documented cause » soit égale à Oui.

Détails :

Si une valeur est manquante pour un des organes atteints lors de la visite V1, la réponse ne peut pas être considérée comme complète. le fait que la valeur est manquante sera documentée.

Si une valeur à la visite d'intérêt est manquante sur un organe non atteint lors de la visite V1, la réponse complète peut être établie, car les réponses complètes ou partielles ne sont établies que sur les organes atteints à V1.

Si « abnormalities present but explained entirely by non-GVHD documented cause » = Oui pour un organe à la visite considérée, le score de cet organe n'est pas corrigé et cet organe n'est pas considéré pour l'évaluation de la réponse complète. cela ne créera pas de valeur manquante pour cet organe et n'empêchera pas la réponse d'être considérée comme complète si les informations sur les autres organes sont disponibles.

- BSA=0 ET skin features=0

M6_GVHD_A_S (préfixe M6 ou C1W6, W14, M9 et M12 selon la visite considérée)

M6_GVHD_A_S_F_S

M6_GVHD_A_S_ABN

- Eyes=0

M6_GVHD_A_E

M6_GVHD_A_E_ABN

- Gastrointestinal=0 (pour chacun des 3 scores : Gastro-oesophageal, Gastro-upper, Gastro-lower)

M6_GVHD_A_GASTRO1

M6_GVHD_A_GASTRO2

M6_GVHD_A_GASTRO3

M6_GVHD_GAST_ABN

- Mouth=0 (considérer la somme des 3 scores : Erythema, Lichenoid, Ulcers)

M6_GVHD_A_MOUTH1
 M6_GVHD_A_MOUTH2
 M6_GVHD_A_MOUTH3
 M6_GVHD_MTH_ABN

Joint and fascia =0

M6_GVHD_A_J
 M6_GVHD_A_J_ABN

Liver : les 3 valeurs (Bilirubine, ALAT et PAL) sont en dessous des ULN (Unité limite supérieure) si le score hépatique était >0 à V1 (table 1 et annexe du protocole)

.<M6_GVHD_A_L_SGPT_V<=M6_GVHD_A_L_SGPT_U_V
 .<M6_GVHD_A_L_ALK_V<=M6_GVHD_A_L_ALK_U_V
 M6_GVHD_LIV_ABN

Le score à V1 est calculé comme :

Score = 0 : Bilirubine normale WITH ALAT AND PAL < 3 UNL

(.<V1_GVHD_A_L_BILI_V<=V1_GVHD_A_L_BILI_U_V et
 .<V1_GVHD_A_L_SGPT_V<3* V1_GVHD_A_L_SGPT_U_V et
 .<V1_GVHD_A_L_ALK_V<3* V1_GVHD_A_L_ALK_U_V)

Score = 1 : Bilirubine normale WITH 3 UNL<=ALAT < 5 UNL AND 3 UNL <=PAL<5 UNL

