Score = 2 : Bilirubine élevée (>1*ULN) mais <= à 3 mg/dL OR ALAT >= 5 UNL OR PAL >=5 UNL (non mentionné dans article NIH).

Score = 3 : Bilirubine élevée > à 3 mg/dL

Lung : si FEV1 >=80% et FEV1<70 à V1. et dans le cas où la valeur de FEV1 est manquante, si le score est égal à 0

M6_GVHD_A_LU_FEV1_V>= 80
 missing(M6_GVHD_A_LU_FEV1_V) and M6_GVHD_A_L=0
 M6_GVHD_A_L
 M6_GVHD_A_L_ABN

Calcul de réponse par organe :

Aucun calcul de réponse **par organe** (complète, partielle ou progression) n'est effectué si :

- « abnormalities present but explained entirely by non-GVHD documented cause » = Oui pour un organe à la visite considérée
- CR_*organe*, PR_*organe* et PD_*organe* sont alors mis à . (manquant)

Aucun calcul de réponse complète ou partielle **par organe** n'est effectué si :

- l'organe n'est pas atteint à V1 ou abnormalities present but explained entirely by non-GVHD documented cause » = Oui pour un organe à la visite V1.
- la progression est recherchée même si pas d'atteinte à V1
- CR_*organe* et PR_*organe* sont alors mis à . (manquant)

- **Partial response by organ:** en se basant sur les mêmes scores et en s'intéressant aux diminutions (ou augmentations) entre V1 (mêmes variables qu'indiquées précédemment mais qui commencent par « V1 » au lieu de « M6 ») et la visite considérée (M6, W6, W14, M9 ou M12)

- une diminution d'1 point pour les scores sur des échelles de 0 à 4 pour : Skin BSA, Skin features, Eyes, Joints, Gastro-oesophageal, Gastro-upper, Gastro-lower,
- une diminution de 2 points pour la somme des 3 sous-scores pour Mouth
- pour Lung, une augmentation entre V1 et la visite d'au moins 10% sur FEV1 avec FEV1 à V1 <70. Dans le cas de FEV1 manquants à V1 et ou M6, une diminution d'1 point sur le score 'lungs'
- pour Liver, (Bilirubine, ALAT ou PAL),
- si les valeurs à M6 sont en dessous des normales, la réponse est considérée Complète
- sinon la recherche d'une réponse partielle est effectuée : diminution de 50% de la valeur initiale
 Le ratio est calculé ainsi : $(M6-V1/V1)*100$ et si le ratio est inférieur à -50 (mais pas de progression pour une des autres valeurs), il y a une réponse partielle

Global Partial response: au moins une réponse partielle sur un organe et avec une absence de progression pour un autre site

- **Progressive disease by organ:**

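### SAP 17.1 scores esophagus, upper GI and lower GI separately but gives them one shared non-GvHD-cause flag, so the computed response can be wrong when the GI sites have different causes

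*SAP*

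**What the plan says.** **Endpoint table.** SAP 8.2.1, repeating Protocol Table 4, has separate rows for esophagus, upper GI and lower GI, each with its own complete-response, partial-response and progression rule. The esophagus row begins "NIH Esophagus Score 0 after previous involvement".

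**Algorithm, scoring.** SAP 17.1 follows that structure. For CR it requires "Gastrointestinal=0 (pour chacun des 3 scores : Gastro-oesophageal, Gastro-upper, Gastro-lower". For PR it lists the sites one by one: "Skin BSA, Skin features, Eyes, Joints, Gastro-oesophageal, Gastro-upper, Gastro-lower". For progression it again names esophagus, upper tract and lower tract.

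**Algorithm, exclusion.** The only exclusion variable listed for the three GI scores is "M6_GVHD_GAST_ABN". When an organ's flag is Yes at a visit, "cet organe n'est pas considéré pour l'évaluation de la réponse complète", and the organ's CR, PR and PD "sont alors mis à . (manquant". A Yes at V1 removes CR and PR for that organ, although progression is still sought.

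**Source form.** Form A (Protocol Appendix 8) has lines reading "Abnormality present but explained entirely by non-GvHD documented cause (specify site/alternate cause", so the paper form asks which site is meant.

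**Reporting.** SAP 11.4.2.1 states: "This table will be completed for skin, mouth, lung, eyes, gastro-intestinal, liver and joint & fascia". That is one gastro-intestinal block, with no rule for combining three site results.

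**The concern.** The algorithm scores by site but excludes by whole tract. Protocol 9.2 says that an abnormality due wholly to another documented cause should not count as involvement. A single flag cannot honor that for one GI site while keeping another site that does have GvHD.

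The stake is the computed response. It feeds sensitivity analyses b and d in SAP 11.4.1.2 with their tables, the by-organ results, and PFS, where SAP 11.4.2.2 takes the event from the global progression rule in 17.1. Analysis b is the check on an investigator-judged endpoint in an open single-arm trial, so its rules should match the endpoint table.

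The single reporting block is a second gap, and it needs no non-GvHD cause to appear: one GI site can improve while another worsens, and the SAP does not say what the row then shows.

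**Working it through.** The plan gives no figure for this point, so the check applies the rules of SAP 8.2.1 and 17.1 to defined cases and then counts patterns.

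**Rules used.** Each GI score runs 0 to 3. Improvement is a fall of at least 1 point; progression is a rise of at least 1 point, except 0 to 1. CR requires all three GI scores to be 0. A ticked flag removes all three. The reference result excludes only the site whose abnormality is wholly non-GvHD.

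**Worked cases, V1 to M6.** Esophageal disease is GvHD and lower GI disease is infection. Scores not shown are 0 throughout.

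| Case | Scores | By site | Unticked | Ticked |
|---|---|---|---|---|
| 1 | esophagus 2 to 1, lower GI 0 to 2, skin 2 to 0 | global PR | improvement plus progression, so PR is blocked | GI dropped, all else 0: global CR |
| 2 | esophagus 2 to 3, lower GI 0 to 2, skin 2 to 0 | progression, non-responder | progression, non-responder | GI dropped, all else 0: global CR |
| 3 | esophagus 1 to 0, lower GI 0 to 2 | GI CR | improvement plus progression | GI result missing |
| 4 | esophagus 2 to 1, lower GI 0 to 1 | GI PR | GI PR | GI result missing |

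In cases 1 and 3 neither setting gives the by-site result. In case 1 the ticked setting keeps the patient a responder but in the wrong category. In cases 2 and 4 the unticked setting is right. So discordant causes do not always produce an error.

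**Counting all GI patterns.** Each site has 4 × 4 = 16 score pairs. A non-GvHD cause at M6 needs an M6 score above 0, which adds 4 × 3 = 12 states, giving 28 per site and 28³ = 21,952 patterns.

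- No non-GvHD cause at any site: 16³ = 4,096 patterns. Unticked is wrong in 0.
- Every involved site non-GvHD: 13³ − 1 = 2,196 patterns. Ticked is wrong in 0.
- Discordant causes: 21,952 − 4,096 − 2,196 = 15,660 patterns. Ticked is wrong in 15,120, unticked in 7,710, and both in 7,182; 7,182 / 15,660 = 46%.

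Here wrong means that the combined GI category differs from the by-site result. The counts weight every pattern equally and are not patient frequencies.

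**Reporting gap.** Among the 4,096 patterns with no non-GvHD cause, each site has 6 improving pairs, 5 progressing pairs and 5 others. Patterns with at least one site improving and another progressing number 4,096 − 10³ − 11³ + 5³ = 1,890. The single block has no rule for these.

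**The case against.** **The flag's own wording.** It applies only where another cause accounts for the whole abnormality. With esophageal GvHD still present, a careful investigator would leave a tract-level flag unticked, and case 2 then comes out right. The key points under Protocol Table 3 take the same line for global severity, where an organ with several causes is still scored. This stands: the false CR in case 2 needs a flag set against its wording. It does not rescue the unticked setting in cases 1 and 3, where wholly infectious diarrhea counts as progression, contrary to Protocol 9.2. That error runs against efficacy but is still an error.

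**One flag has precedent.** Protocol 9.2 lists the GI tract as one organ site and Appendix 2 has one GI flag. However, 9.2 goes on to score the three parts separately, as do Table 4 and SAP 17.1. The eCRF is not among the documents, so it is unproven that the database holds the site text. The fix needs a fallback for that reason.

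**Overlap at month 6 may be uncommon.** Protocol 11.8 lists nausea, vomiting and diarrhea as frequent with ATO. But a second cycle starts by week 11 and lasts 4 weeks, so scheduled ATO ends by about week 15, roughly 11 weeks before month 6, and Form A asks about the past week. This is fair for ATO effects at M6. It is weaker for the week 6 and week 14 visits, set two weeks after a cycle, which can supply a first progression date for PFS. It does not address infection.

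**Does GI worsening fail to block a global PR?** A reader might infer this from the single reporting row. The documents do not support it. SAP 17.1 names the three sites for progression, requires no progression at another site for global PR, and defines global progression by any one site. The row is a reporting gap and does not show that scores are merged.

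**Conclusion.** The mismatch is real and narrow. Where GI sites share a cause, a correctly set flag gives the right answer. Where causes differ, the algorithm as written can misclassify the GI result, and in 46% of the enumerated discordant patterns no setting of the flag is right. A reader might infer that GI response is miscomputed however the flag is set; the zero-error counts for concordant causes and cases 2 and 4 show otherwise.

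The main primary analysis is untouched, because SAP 11.4.1.1 takes the investigator's judgement. A reader might also infer that one affected patient turns success at 17 of 21 into failure at 16 of 21. That does not follow: analyses b and d repeat the Clopper-Pearson rule of 11.4.1.1, and the lower 95% bounds are 58.1% and 52.8%, both below 60%, so the decision is the same. At other counts one patient could move that bound across 60% (18 of 21 gives 63.7%), but only in a sensitivity analysis. The sample size is not affected.

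The conclusion assumes that the database carries one GI flag per visit, as 17.1 lists. The number of patients with discordant GI causes is not given and could be zero. It is worth correcting before lock because the rule contradicts the endpoint table it implements.

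**What to change.** In SAP 17.1, at V1 and at each visit, apply the non-GvHD exclusion only to the GI score (GASTRO1, GASTRO2 or GASTRO3) named in the Form A site and cause text. Keep site-level CR, PR and PD feeding the global response, as the algorithm already does for scoring. In 11.4.2.1, replace the single gastro-intestinal block with three: esophagus, upper GI and lower GI. If the database holds no site text for a flagged patient, run the computed response both ways, once excluding all three GI scores and once excluding none, and report both.

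The cost is a short SAP change, a few lines of code, reading the site text for flagged patients before lock, and two more blocks in the by-organ table. No new data collection is needed if the Form A text was captured.
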